#### 13.4.1 Projected recruitment and retention rates

We have estimated from site feasibility analysis that the sites' recruitment targets (couples) will be as follows:

- Leeds (6.7% or 250)
- Guys (18.5% or 690)
- Bart's & The London (12.1% or 450)
- Manchester (7.7% or 288)
- Birmingham (6% or 224)
- Sheffield (4.3% or 161)
- Dundee (3.8% or 143)
- Aberdeen (3% or 113)
- Coventry (5.6% or 209)
- Leicester (3.1% or 115)
- Homerton (7.5% or 279)
- IVF Hammersmith (5.4% or 200)

Other sites will be recruited as required.

A 10% loss to follow-up (the worst-case scenario) will still ensure outcomes for 3357 primary treatment cycles, which is sufficient to power the study at even 5% improvement per couples undergoing a fresh ICSI treatment cycle. It is anticipated, however, that compliance with follow-up will be high given the lateness of randomisation and the routine nature of collecting pregnancy outcome data in this population (refer to Study Flow Diagram – Appendix 3).

[figure not shown]
#### 13.5 Sample size - Mechanistic evaluation

The sample size for the clinical trial (3,730) is based on detecting a 5% improvement in live birth outcome at 90% power (3,266). In contrast, the mechanistic sample size is based on an estimated minimum of 180 required for logistic regression analysis of the relationship between HBS and clinical outcomes  and can therefore be far smaller. While this number accommodates the potentially limiting availability of samples with low (<50%) HB scores (estimated at ~10% or ~370), it is a minimum estimate that does not satisfy the need to more accurately specify the relationships between the mechanistic and clinical outputs of this study that are less dependent on HB scoring (such as sperm concentration). Furthermore, as indicated elsewhere, many of the samples will not be amenable to mechanistic tests. Hence, the chosen mechanistic sample size is a balance between minimum sample size requirements (180) required to link clinical and mechanistic outcomes, the need to access more samples in order to accommodate limitations in their use and the relative cost of analysis. Assuming that  $\sim$ 20% of samples can be examined by one or more tests based on cytology, only 36/180 will satisfy the criteria. Hence ~900 samples (180/36\*180) are required overall. All mechanistic tests are needed to facilitate the identification of the form of damage that compromises sperm function in relation to clinical outcome (Fig 6).

All samples will be transferred to the Human Biomaterials Resource Centre, University of Birmingham as outlined in Section 11.9 for initial cytology. Cytology will be performed retrospectively on as many of the 3730 trial samples as required for mechanistic analysis. It will provide an important first step characterisation on the integrity of the semen samples. The rationale for banking semen samples on all trial participants is based on maximising the success of the exploratory mechanistic components of the study. The sampling has been described in Section 11.9.1. In summary, the mechanistic evaluations will be performed retrospectively following PCTU stratification by sample characteristics based primarily on the HBS to assay across the three, <50%, 50-65%, >65% HBA scoring strata, with the cytology secondarily determining if there is sufficient sample available. It is anticipated that a significant proportion of semen samples will be identified as having insufficient sperm for further mechanistic evaluation. The retrospective stratification will generate a balanced sampling

frame from each trial arm to obtain high quality information for each test in each stratum even if only a fraction of the samples is amenable to global examination by *all* tests (refer to Figure 5; Table 3).

Of note the mechanistic tests do not inconvenience participants, or their management or treatment as they use residual semen samples from the ISCI/PICSI IVF procedure.

**Figure 6**. Schematic representation of structural equation modelling showing relationship between measured quantities (boxes) and latent variables (ellipses). *DNA frag* and *Chrom* are treated as covariates in the regression model for HBS score.

## 13.6 Statistical Analysis

## 13.6.1 Clinical Evaluation

Our unit of analysis will be couples randomised to alternative interventions. In addressing the research question in this grant application, we have elected to focus on the outcome of the ICSI cycle with first fresh embryo transfer in each randomised couple and powered the trial accordingly. We believe that, if effective, the impact of the intervention will be evident in the first fresh study cycle. Attempting to evaluate cumulative live birth rates after an ICSI treatment culminating in transfer of fresh embryos followed by the subsequent transfer of frozen embryos in those not achieving a pregnancy would require an extended duration of follow-up. This would significantly increase the complexity and costs of the proposed trial, without generating outcomes of sufficient additional value.

Numbers of couples who are eligible, recruited, and followed up will be recorded in a CONSORT flow-chart. Baseline characteristics of couples in each arm will be tabulated. Outcomes in intervention and non-intervention arms will be compared using multivariable regression with effects summarised as odds ratios with 95% confidence intervals.

If there is evidence that the clinical pregnancy rate differs between the trial arms, then secondary analyses will be carried out taking only women with a clinical pregnancy as the denominator.

Sensitivity analyses will be carried out which adjust for other potentially prognostic factors in addition to the minimisation factors. Factors to be included will be selected blind to their distribution between recruitment arms or the effect of treatment on outcome, and will be those that are associated with the outcome or believed a priori to be prognostic.

In all cases, results of primary analyses will be given more weight than those of the secondary analyses.

**Subgroup analyses.** For binary outcomes, results will be expressed as odds ratio with 95% confidence intervals of pregnancy success in either arm. The exploratory subgroup analyses

- Hyaluronan Binding Score; HBS (High (>65%) versus low (≤65%)),
- maternal age (≤35 years versus >35),
- Previous miscarriages (none versus any),
- FSH hormone level (<6.0miU/ml versus ≥6.0miU/ml ) or AMH hormone level (<17pmol/L versus ≥17pmol/L) where FSH testing is not available.
- sperm concentration (<15mml versus ≥15mml).
- We may also analyse a very low (≤25%) vs. low (>25%, ≤65%) HBS sub-group.

In each case, an interaction test will first be used to determine whether there is a basis for investigating treatment efficacy within subgroups. Sub-group analyses results will be treated with caution, and will be undertaken in relation to the advanced analytical assays summarised in section 13.7 solely for the purposes of hypothesis generation.

As the two arms of this study are compatible with the equivalent arms of the US NIH trial (NCT00741494) they can be included in any future meta analysis of the data.

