## 5.4.3 Risks and benefits

Hyaluronan is a natural polymeric secretion of the cervical mucus and cumulus-oopherus complex and so poses no known risks to the egg or zygote. PICSI – HA based selection system has been CE approved for use and no risks have been identified by the manufacturer. However as a precaution against possible adverse effects of intervention such as early pregnancy loss or preterm labour we will conduct a safety monitoring interim analysis. PVP is an inert synthetic polymer that is used extensively in the food and pharmaceutical industries with no known adverse side effects. It is used in almost every ACU as a viscous retardant of sperm motility, making it easier for a skilled practitioner to isolate and prepare a single sperm for ICSI. The advantage of switching to hyaluronan is likely to be threefold.

**Firstly**, sperm bind to HA, effectively immobilising them long enough to be picked up. **Secondly**, HA is thought to work by selectively binding sperm of a higher quality allowing the embryologist to wash away non-adherent sperm before the choice of sperm for pick-up is made.

**Thirdly**, although the trained embryologist can be very good at selecting the 'right' sperm for injection HA should remove any subjective operator selection and allow consistent objective selection of the 'right' sperm for injection.

The main benefits expected of switching to HA are a decrease in early pregnancy loss and a subsequent increase in LBR at normal term. We consider that HA selection will be beneficial to couples where semen quality is too poor for IVF and may also have a significant benefit for older women with poorer quality eggs that have a decreased potential to repair sperm DNA damage. Couples participating in this research study will benefit the community by increasing the knowledge base of clinical and scientific improvements in the effectiveness of ICSI procedures.

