## 6.1.2 Secondary Objectives

## 6.1.2.1 *Clinical:*

To determine the impact of PICSI-selected IntraCytoplasmic Sperm Injection (PICSI) versus PVP ICSI on:

- increasing clinical pregnancy (CP) rate based on detection of fetal heartbeat or presence of fetal sac at 6-9 weeks' gestation
- reducing miscarriage rate defined as pregnancy loss after confirmation of clinical pregnancy,
- increasing LBR at <37 weeks' gestation.

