## 13.2.2 Secondary endpoint analyses

The secondary endpoints are the respective proportions of women who:

- experience a clinical pregnancy based on presence of fetal heartbeat or fetal sac at 6-9 weeks' gestation
- experience a clinical pregnancy and miscarry
- experience a clinical pregnancy and proceed to a live birth <37 weeks

These proportions have as their denominator the number of women who are followed up after their first ICSI cycle post randomisation, and as their numerator the number with the respective outcome. The proportions of each will be compared between arms using multivariable logistic regression adjusting for centre and for factors used in the minimisation. An odds ratio with 95% confidence interval will be calculated.

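### Loss per clinical pregnancy is analysed only if pregnancy rates appear to differ, a poorly aimed trigger; the objective for live birth before 37 weeks also points the wrong way

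*Protocol*

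**What the plan says.** **Main analysis (section 13.2.2).** The miscarriage endpoint is the proportion of women who "experience a clinical pregnancy and miscarry". Live birth before 37 weeks is built in the same way. On the denominator: "These proportions have as their denominator the number of women who are followed up after their first ICSI cycle post randomisation". Both are compared by logistic regression adjusted for centre and the minimisation factors, giving an odds ratio and 95% confidence interval.

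**Conditional addition (section 13.6.1).** "If there is evidence that the clinical pregnancy rate differs between the trial arms, then secondary analyses will be carried out", and these are done "taking only women with a clinical pregnancy as the denominator". The protocol gives no test, level or direction for what counts as evidence. The same section adds that "results of primary analyses will be given more weight than those of the secondary analyses", which I read as ranking the triggered analyses below the per-woman ones.

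**Objectives and risks.** Section 6.1.2.1 lists raising the clinical pregnancy rate, "reducing miscarriage rate defined as pregnancy loss after confirmation of clinical pregnancy" and "increasing LBR at <37 weeks' gestation". Section 5.4.3 justifies a safety interim analysis as a precaution against "possible adverse effects of intervention such as early pregnancy loss or preterm labour".

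**The concern.** The per-woman miscarriage proportion is the clinical pregnancy rate multiplied by the loss risk per pregnancy. The trial hopes to raise the first and lower the second, so success on one objective works against the other in this endpoint. The loss risk per pregnancy isolates the second effect. It is also the form of the Table 2 evidence that motivates the trial, yet the adjusted estimate of it is produced only if a different outcome appears to differ.

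The condition also points the wrong way. If pregnancy rates are alike, the pregnant women in the two arms are more likely to be comparable, and the supporting analysis is omitted. If pregnancy rates differ, treatment has probably changed who becomes pregnant, and the analysis is run without any stated caveat.

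A separate drafting conflict concerns live birth before 37 weeks. As section 6.1.2.1 is worded, a rise in preterm births would meet an efficacy objective, while section 5.4.3 names preterm labour as a possible harm. The endpoint can rise because losses became preterm births, because term births became preterm, or simply because more women conceived. It has no clear favourable direction on its own.

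**Working it through.** **Inputs from the protocol.** 1:1 allocation (9.5). 3,730 couples with 10% loss gives 3,730 × 0.9 = 3,357 (13.4.1), about 1,678 per arm. Table 2 (5.3.2), order taken as PVP / PICSI: clinical pregnancy 47.8 / 47.3% and miscarriage per pregnancy 10.0 / 4.3% for all scores.

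**Assumptions.** Two-sided 5% and a trigger at p<0.05, since the protocol gives no level. The two-sided 5% fits its sample size: taking 24% (5.1) against 29% at 90% power, (1.960 + 1.282)² × (0.24×0.76 + 0.29×0.71) / 0.05² = 10.507 × 0.3883 / 0.0025 ≈ 1,632.01, so 1,633 per arm or 3,266, as stated in 13.5. The protocol gives no effect size for miscarriage. Rates below that are not from Table 2 are illustrations.

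**Step 1. The protocol's own rates.** Per-woman risk = C × m, where C is the clinical pregnancy rate and m the loss risk per pregnancy.
- All scores: 0.478 × 0.100 = 4.78% against 0.473 × 0.043 = 2.03%. Odds ratio 0.41 per woman, 0.40 per pregnancy.
- HBS >65%: odds ratio 0.68 per woman, 0.74 per pregnancy.
- HBS ≤65%: 7.0% against 0% per woman.

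Nothing is masked here.

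**Step 2. An untriggered case.** Pregnancy 30% against 33%: z = 0.03 / √(2 × 0.315 × 0.685 / 1,678.5) = 1.87, so the trigger does not fire. Loss per pregnancy 15% against 12% is a ratio of 0.80. Per woman it is 0.30 × 0.15 = 4.50% against 0.33 × 0.12 = 3.96%, a ratio of 0.88. A 20% fall appears as 12%.

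**Step 3. When the per-woman result reverses.** It reverses if m₁/m₀ > C₀/C₁. For 35% to 40% the break-even fall in loss is 1 − 35/40 = 12.5%. With loss 10% to 9%, the per-woman risk goes from 3.50% to 3.60% (odds ratio 1.03, against 0.89 per pregnancy). But here z = 0.05 / √(2 × 0.375 × 0.625 / 1,678.5) = 2.99, so the trigger fires and the per-pregnancy result is reported.

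The largest observed pregnancy-rate rise that leaves the trigger unfired is about 3.2 points from 35% and 3.4 points from 47.8%. The break-even falls are then 1 − 35/38.2 = 8.4% and 1 − 47.8/51.2 = 6.6%. Untriggered reversal therefore needs a relative reduction in loss smaller than about 7 to 8%.

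**Step 4. How often the estimate is skipped.** Probability that the trigger fires, for control pregnancy rates of 35% to 47.8%:

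| True gain | Trigger fires |
|---|---|
| 2 points | 21–23% |
| 3 points | 41–44% |
| 4 points | 64–67% |
| 5 points | 83–85% |

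For pregnancy 35% to 38% and loss 10% to 8%, the odds ratio is 0.86 per woman and 0.78 per pregnancy, with power of 11% and 23%. The per-pregnancy analysis is skipped 1 − 0.44 = 56% of the time.

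**Step 5. Table 2's loss rates with added pregnancy gains.** With loss 10.0% to 4.3%, pregnancy 47.8% to 52.8% gives odds ratio 0.46 per woman against 0.40 per pregnancy. Pregnancy 47.8% to 57.8% gives 0.51 against 0.40. Per-woman power stays at about 98% and 95%.

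**The case against.** The case for leaving the text alone is substantial.

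- **The main analysis is fixed.** A reader might infer that a data-dependent rule chooses the miscarriage result. It does not: section 13.2.2 sets the per-woman analysis unconditionally, and the triggered analysis is additional and ranked lower. This stands.
- **The per-woman denominator is not an error.** It keeps the randomised comparison among women followed up. This stands, and the fix retains it.
- **Reversal is mostly guarded against.** A reader might infer that a real benefit could be reversed and go unseen. Reversal needs a rise in pregnancy rate, which is what fires the trigger. Outside the narrow band in Step 3, the documents do not support that reading.
- **The skipped analysis may change little.** In the Step 2 case, loss per pregnancy (about 504 against 554 pregnancies) gives z ≈ 1.43 and per woman z ≈ 0.78, so neither is significant. This stands for significance. The size of the estimate still differs.
- **Crude rates can be derived.** Pregnancies and miscarriages are both reported by arm, so a reader can divide one by the other. The adjusted odds ratio and its interval cannot be recovered that way.
- **The threshold may be in the analysis plan.** It may, and its absence here is not the complaint. Any threshold leaves the rule data-dependent and aimed the wrong way.
- **The objective's wording alters no analysis.** Sections 13.1.2.1 and 13.2.2 state the outcome neutrally. True, but the objective governs how a result is read.

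**Conclusion.** The point holds as a minor one. The rule in section 13.6.1 makes a useful supporting estimate depend on another outcome, and supplies it when conditioning on pregnancy is least clean. The consequence is attenuation and a missing adjusted estimate for pregnancy-rate gains of about 2 to 4 points. It is not a hidden or reversed main result. These sizes rest on assumed pregnancy and loss rates, about 1,678 women per arm and a trigger at two-sided p<0.05; with the protocol's own Table 2 rates nothing is masked. The conflict between sections 6.1.2.1 and 5.4.3 over live birth before 37 weeks rests on the wording alone and needs no assumption.

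**What to change.** 1. In section 13.6.1, delete the condition on the clinical pregnancy rate.
2. Keep the per-woman comparison in section 13.2.2 as the main analysis of miscarriage and live birth before 37 weeks.
3. Always report the adjusted per-clinical-pregnancy odds ratio and 95% confidence interval beside it, labelled as conditional on a post-randomisation event and therefore not a clean randomised comparison.
4. Reconcile section 6.1.2.1 with section 5.4.3 by stating the objective neutrally, as the effect on live birth before 37 weeks.
5. Show live birth at any gestation (37 weeks or more plus before 37 weeks) beside it.

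The cost is a few more table rows, one reworded objective and a conditional estimate that must carry its caveat. No new data are needed.

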## 5.4.4 Justification

- There is a need to increase LBR at term for IVF and IVF-ICSI patients by reducing fertilisation failure and miscarriage rate.
- Male fertility is thought to be declining through a reduction in sperm counts across the globe since WWII .

- The number of IVF and ICSI procedures is rapidly increasing and in particular, ICSI is being increasingly used for reasons other than treating male infertility (it now accounts for >50% of all IVF cycles), hence the selection of high quality sperm becomes a more urgent priority.
- Average LBR for IVF and IVF-ICSI have reached a plateau at 24% (although success rates vary widely across clinics and younger couples are generally more successful).
- Lower rates of fertilisation and higher rates of pregnancy loss following ICSI procedures are likely to generate higher costs as its use widens beyond treatment for male infertility. Wider use of ICSI without appropriate and adequate safeguards could lead to a future increase in the incidence of deleterious gene lesions in the wider population.
- The largest clinical trial so far, involving nine US centers has shown efficacy for PICSI in increasing CPR (10%) and a corresponding reduction in miscarriage rate (10%). A smaller Italian trial reported an encouraging 5% improvement in LBR following HA-based selection (using a non-optimised HA containing solution).
- Of the two commercially available HA-based selection systems, PICSI can be introduced into the ART procedure with minimal training and without any additional intervention and is the only product shown so far to have clinical efficacy in improving CPR.
- HA-based selection overcomes the highly subjective assessment of sperm quality used by the practicing embryologist to choose the 'right' sperm for injection.

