## 6.1.1.2 *Mechanistic:*

Evaluate if PICSI can compensate for poor sperm quality and investigate HBS in relation to chromatin integrity and LBR. Evaluate the differences in chromatin architecture in DGC washed and pelleted sperm with high and low HBS including any correlation with DNA damage.

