#### 9.5 Randomisation Procedures:

Following screening and formal enrolment onto the study, confirmation of eligibility and completion of baseline assessments the female participant will commence egg stimulation and the couple will enter the IVF clinical care pathway. At the couples' visit for the IVF procedure, approximately 2-8 weeks following enrolment, couples will be randomised into the trial. The time interval between enrolment and randomisation is centre dependent as they will be following local practice for egg simulation which precedes IVF. Couples will be randomized 1:1 to interventional (PICSI) and the non-interventional (PVP-ICSI) arms. Randomisation into the study will be typically on the day of the ICSI/PICSI and will be performed by an authorised member of staff at the research site, using the web 24-hour automated randomisation system developed by PCTU. Each centre will be provided with a unique set of log-in usernames and passwords for the study staff to do this. Online randomisation is available 24 hours a day, 7 days a week apart from short periods of scheduled maintenance. The randomisation system will generate intervention arm allocation to the couple which will be recorded on the Randomisation and Intervention Form.

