## 13.2 Endpoint analyses

## 13.2.1 Primary endpoint analysis

The primary endpoint is the proportion of women randomised who experience a live birth  $\geq$ 37 weeks. This proportion has as its denominator the number of women who are followed up after their ICSI cycle with first fresh embryo transfer post randomisation per arm and as its numerator the number of women who conceive and proceed to have a live birth  $\geq$ 37 weeks as

a result of their first fresh ICSI cycle. The proportion will be compared between arms using multivariable logistic regression adjusting for centre and for factors used in the minimisation. An odds ratio with 95% confidence interval will be calculated.

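### Protocol 13.6.1 uses an interaction test as a gate on examining effects within prespecified subgroups, so published stratum estimates would depend on a large observed interaction

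*Protocol*

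**What the plan says.** Section 13.6.1 names the exploratory subgroups: HBS above 65% against 65% or below, maternal age, previous miscarriage, FSH or AMH, and sperm concentration, with an optional very-low HBS split. Results are to be given as odds ratios with 95% confidence intervals. The next paragraph sets an order of work that applies to each of them: "an interaction test will first be used to determine whether there is a basis for investigating treatment efficacy within subgroups". It gives no level for that test and does not say what is tabulated if the test finds no such basis. It asks for caution and limits the subgroup results to hypothesis generation.

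Three other places give the HBS split its weight:

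- Section 6.1.1.2 makes it a primary mechanistic objective to "Evaluate if PICSI can compensate for poor sperm quality".
- Section 5.3.2 and Table 2 report that the earlier US trial had its best results at HBS ≤65%.
- Section 13.6.1 says of the trial's two arms, in relation to that US trial, that "they can be included in any future meta analysis of the data".

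**The concern.** Testing for interaction and deciding whether to produce stratum estimates are separate steps. Here the first controls the second. If the gate stays shut, the plan promises no treatment effect for low-HBS couples, although section 10.1 has HBS measured in both arms. If it opens, it does so because the observed contrast was large, so the estimates then shown are biased away from the null on average. A reader of the published subgroup results would see a selected set, and the objective on poor sperm quality would be informed by that set.

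**Working it through.** **Inputs**

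- Outcomes: 3,730 less 10% = 3,357 (section 13.4.1: "A 10% loss to follow-up (the worst-case scenario) will still ensure outcomes for 3357 primary treatment cycles"), allocated 1:1 (section 9.5).
- Control live birth rate: 24% (section 5.4.4), assumed equal in both HBS strata.
- Share at HBS ≤65%: not stated for this trial. Table 2 gives 121/(121 + 357) = 25%. Section 13.5 puts about 10% below 50%, which serves as a low end.
- Gate level: not stated. I assume two-sided 0.05, in line with section 13.2.1 ("An odds ratio with 95% confidence interval will be calculated").
- Live birth effect by HBS: not stated. I assume low-minus-high gaps of 5 and 10 points, either with no benefit at high HBS or with the overall gain held at the design value of 5 points.

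**The plan's own figure.** For 24% against 29%, 90% power and two-sided 0.05, n per arm = (1.960 + 1.282)² × (0.24×0.76 + 0.29×0.71) / 0.05² = 1,632 to 1,633. Rounded up and doubled this is 3,266, the protocol's figure. It powers the overall comparison only.

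**Formulas**

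- Stratum variance: s² = [p0(1−p0) + p1(1−p1)] / (n/2).
- SE of the contrast: t = √(s_low² + s_high²).
- Chance the gate opens at true gap δ: P = Φ(δ/t − 1.96) + Φ(−δ/t − 1.96).
- Mean contrast given that it opens: δ + t[φ(1.96 − δ/t) − φ(1.96 + δ/t)]/P.
- Mean low-HBS effect given that it opens: true effect + (s_low²/t²) × (mean contrast − δ).

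**Worked case: low +5, high 0, 25% share (839 and 2,518 couples)**

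- s_low² = (0.1824 + 0.2059)/419.6 = 0.000925.
- s_high² = (0.1824 + 0.1824)/1,259 = 0.000290.
- t = √0.001215 = 0.0349, so δ/t = 1.43 and P = Φ(−0.53) = 0.30.
- Mean contrast given opening = 0.05 + 0.0349 × 0.346/0.30 = 0.090.
- Mean low-HBS effect given opening = 0.05 + 0.76 × 0.040 = 0.081, which is 1.6 times the truth.

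| Low / high gain (points) | Gap | Gate opens | Mean contrast if open | Low-HBS effect if open |
|---|---|---|---|---|
| +5 / 0 | 5 | 30% | 9.0 | 8.1 (×1.6) |
| +8.75 / +3.75 (overall +5) | 5 | 29% | 9.2 | 11.9 (×1.4) |
| +10 / 0 | 10 | 80% | 11.2 | 10.9 (×1.09) |
| +12.5 / +2.5 (overall +5) | 10 | 80% | 11.3 | 13.5 (×1.08) |
| +12.9 / −4.9 (Table 2 clinical pregnancy pattern) | 17.8 | 99.9% | 17.8 | 12.9 (×1.00) |

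**Odds-ratio scale.** The protocol specifies odds ratios. Repeating the first four rows with log odds ratios and s² = 1/[(n/2)p0(1−p0)] + 1/[(n/2)p1(1−p1)] gives opening rates of 29%, 26%, 78% and 74%. The low-HBS log odds ratio is inflated 1.6, 1.4, 1.10 and 1.09 times.

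**Sensitivity to the HBS share.** At a 10% low-HBS share, the risk-difference formulas give about 16 to 17% opening at a 5-point gap and about 48 to 49% at a 10-point gap.

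**Sensitivity to the gate level.** On the odds-ratio scale, with overall +5 and a 25% share, a low/high gain of +7.5/+4.2 opens the gate 14% of the time at a level of 0.05 and 23% at 0.10. For +10/+3.3 the figures are 42% and 55%.

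**With the gate removed.** For a 25% share, the low-HBS odds ratio would carry a 95% interval of about ×/÷ 1.35, with no selection from the gate and no change in sample size.

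**The case against.** The case against has real force, and several stronger readings that a reader might draw are not supported.

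- **That the low-HBS effect is withheld in most plausible cases.** The protocol states no live birth effect by HBS, so this cannot be shown. Under the only HBS-specific treatment effects it cites for pregnancy, the gate opens almost always. That pattern implies an overall effect of 0.25 × 12.9 − 0.75 × 4.9 = −0.45 points and concerns clinical pregnancy, so it sits badly with a design gain of 5 points in term live birth. It still shows that the answer depends on the scenario.
- **That the low-HBS effect is nearly doubled when shown.** The 1.8-fold figure (9.0/5) belongs to the low-minus-high contrast. The low-HBS effect itself is inflated about 1.4 to 1.6 times at a 5-point gap.
- **That the US benefit was confined to HBS ≤65%.** Table 2 also shows implantation (34.8/37.9) and miscarriage (7.8/5.9) favouring PICSI above 65%. Only clinical pregnancy went the other way (51.1/46.2).
- **That later pooling gets only selected results.** Section 16.2 allows anonymous data to be shared for individual patient data meta-analysis, so a pooler could compute every stratum. The meta-analysis remark in 13.6.1 concerns the arms, not published subgroup estimates.
- **That the trial depends on this estimate.** The sample size and primary clinical objective concern overall live birth at ≥37 weeks, and the subgroups are labelled exploratory. The mechanistic objective also has its own model in section 13.7, with HBS as a covariate for outcome. That model describes no treatment-by-HBS term, so it does not fully replace the stratum estimates.
- **That nothing is reported after a failed test.** This is implied, not stated, and an SAP might tabulate all strata.

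The sequence in 13.6.1 stands despite all this. It is a rule fixed in the protocol for every listed subgroup, and an SAP that investigated all strata regardless would depart from it.

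**Conclusion.** The point holds as a minor improvement. A gate on estimation makes the published stratum effects conditional on a large observed interaction. The consequence is material for moderate differences in effect, of around 5 points. At 10 points about one trial in five would still stop at the gate, but inflation is slight, and at larger gaps the issue nearly disappears. These sizes rest on the assumed 25% HBS share, 24% control rate in both strata, 5% gate level and chosen gaps. A smaller low-HBS share makes the filter stricter. The primary analysis and the sample size are not affected. What is affected is the published subgroup evidence, in particular that bearing on whether PICSI compensates for poor sperm quality.

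**What to change.** Replace the gating sentence in section 13.6.1. For every prespecified subgroup, report the odds ratio with 95% confidence interval in each level, together with the interaction estimate, its interval and its p-value, whatever the interaction result. State that any claim of differing effects rests on the interaction only. Keep the existing caution and the restriction to hypothesis generation.

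The cost is one sentence and one forest plot, with no extra data or couples. The downside is that some readers may over-read individual strata. The interaction estimate printed beside them limits that risk.
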